#### **Analysis of deaths and other serious adverse events**

A listing of deaths will be provided.

A summary table of the other serious adverse events should be provided. In case of low incidence of serious adverse events, only a listing will be done.

#### Vital signs, ECG, physical examination and laboratory data:

Vital signs (SBP, DBP, heart rate, T°), ECG, physical examination and laboratory data will be described at each visit/time. Changes from baseline will be described. Abnormal values will be identified in subject data listings.

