**Table 3. Study Plan – Part B (Groups 3 to 8).**

Groups 3 to 8	Screening		Assessment Period												FU Visit	EOS Visit
	D-14 to D-2	D-1	Predose	H0	H1	H2	H3	H4	H5	H6	H7	H8	H10	H24		
	D1												D2	D8±1	D28±2	
SCREENING PROCEDURES																
Signature of the informed consent	X															
Medical history	X	X														
Prior medications	X	X														
Physical examination	X	X 												X 	X 	X 
Viral Serology	X															
Alcohol breath test & Urine Drug Screen	X	X														
Inclusion / exclusion criteria	X	X														
Randomisation				X												
24h Holter	X															
Hospitalisation																
Study treatment schedule				i.v. loading dose T0 to T15'												
Meals 		X										X			X	
SAFETY ASSESSMENTS																
Vital signs  (including BMI assessment at screening)	X	X	X	T0', T10', T20, T30, T40, T50'	X	X	X	X	X	X	X	X	X	X	X	X
ECG	X	X	X	T15'	X								X	X	X	
Telemetry 			X													
Haematology	X	X		T15'				X							X	
Coagulation	X	X		T15'				X							X	
Serum chemistry	X	X		T15'				X							X	
Urinalysis	X	X													X	
Infusion site assessment			X	T15' (6)	X	X		X		X		X			X	
Anti-LR12 antibody screening 			X												X	X
Pharmacokinetics 			X	T5', T15', T18', T30', T45'	X	X		X		X			T-15, T2', T4', T7', T15', T30	X		
Adverse Events	←														→	
Concomitant medication	←														→	

(1) Brief physical examination.

(2) Standard meals will be served at standard times. Meal at dismissal will be optional.

(3) Time of procedures is relative to the start of infusion.

(4) Tympanic temperature will be collected at pre-dose and at H8 only. Vital signs at H0 and H8 will be measured only in supine position.

(5) 12-Lead telemetry will be recorded from pre-dose to 10 h post-dose.

(6) The check of the local tolerability at H0 should be performed just after the loading infusion.

(7) PK sampling performed at the end of the 8 hours i.v. infusion will be as follows: 15 min before H8 (T-15'), then during 30 min after the end of the infusion as specified in the table. H0 timings refer to start of infusion.

---

(8) Should any subject develop ADA against LR12, they will be followed up for at least 3 months or until the antibody response is no longer detected.

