### 9 SELECTION AND WITHDRAWAL OF SUBJECTS

#### 9.1 Number and Source of Subjects

26 subjects are planned (i.e. 2 first groups of one healthy male subject each and 6 groups of 4 healthy male subjects). The number of subjects in a dose cohort can be extended to gather further information on a dosing regimen, withdrawn subjects can be replaced at the discretion of the sponsor and investigator, if not withdrawn for safety reasons and replacement subjects may be enrolled in an ongoing cohort, or dosed together as a group or dosed separately. The total number of subjects will not exceed 72 subjects (Table 9).

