## 9.5 Subject Inclusion and Randomisation

Subjects in this study will be assigned to a treatment regimen according to a randomisation schedule generated by a statistician using PROC Plan. Details regarding the unique screening and subject number will be included in the SOM.

For Part B (Groups 3 to 8), eligible subjects who meet the eligibility criteria will be randomly assigned on Day 1. Subjects will be randomly assigned in Part B (Groups 3 to 8) in a 3:1 ratio to either MOTREM (LR12) or Placebo.

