## **12.3 Electrocardiographic (ECG) Measurements**

### **12.3.1 Recording of 12-lead ECGs**

12-lead ECGs will be recorded at the time-points described in Study Plan (Table 2 and Table 3) using a GE Marquette MAC1200® /MAC1200ST® recorder connected via a fixed network connection to the MUSE® Cardiology Information System (MUSE). ECGs recorded during screening will be stored electronically on the MUSE information system. Only ECG recorded electronically will be valid ECG for any purpose other than safety assessment. ECG printouts may be filed in the subject's CRF for medical safety reviews.

Each ECG recorder will be set up to the required technical specifications and containing the information required to identify the records. Each ECG recording will be clearly identified (Subject ID, visit date, and the actual times of ECG recordings).

12-lead ECG recordings will be made after the subjects have been resting in a supine position for at least 10 minutes. The subjects will avoid postural changes during the ECG recordings and clinical staff will ensure that subjects are awake during the ECG recording.

At each time point, the ECG will be recorded in triplicate, to reduce variance and improve the precision of measurement. The triplicates will be performed at approximately 1-minute intervals. Each ECG recording (trace) will last 10 seconds. Repeat ECG will be performed until at least three 10-second ECG records per scheduled time-point meet the quality criteria set out in the SOM and the applicable SOP so to enable reading and analysing at least 5 complexes per derivation.

All recorded ECG will be reviewed by a Research Physician and the review be documented in the CRF. With regards to the clinical assessment of QTc interval, QTcB will be assessed as this is automatically calculated by the equipment. If there is any indication of potential significant QTcB prolongation, QTcF will also be calculated and assessed by a Research Physician. If a subject shows an abnormal ECG, additional safety recordings (including the use of 5 or 12 lead Holter equipment) may be made and the abnormality be followed to resolution if required. Further details will be included in the SOM.

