## **15 STATISTICAL METHODS PLANNED AND DETERMINATION OF SAMPLE SIZE**

### **15.1 Statistical and Analytical Plans**

The analysis will be computed with SAS Version 9.4 (Copyright© 2013 by SAS Institute Inc., Cary, NC, USA).

The statistical analysis plan will be agreed by the sponsor.

Individual data listings will contain all available results. They will be presented by IMP (LR12 vs Placebo), dose group (Group 1-Group 8), subject number and time point if applicable.

Descriptive statistics will be presented by IMP and time point.

All relevant data will be summarised as follows:

- Quantitative endpoints will be presented in terms of mean, standard deviation, median, Q1, Q3, extreme values, number of subjects and missing data.
- Qualitative endpoints will be presented in terms of number and percentage of each modality and number of subjects and missing data.

For quantitative endpoints, Student test for parametric tests or Wilcoxon test for non-parametric tests will be used.

For qualitative endpoints, Chi-square test for parametric tests or Fisher Exact test for non-parametric tests will be used.

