**Revised text**

Table 3

Pharmacokinetics on Day 1 H0: T5', T15', T18', T30', T45'

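### ECG change is summarised by treatment and time point only, averaging six regimens, and is never related to the LR12 concentrations measured at the same nominal times (T15' and H1)

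*Combined protocol and SAP*

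**What the plan says.** - Section 15.1.3, on vital signs, ECG, physical examination and laboratory data: "ECG, physical examination and laboratory data will be described at each visit/time. Changes from baseline will be described".
- Section 15.1 sets the grouping: "Descriptive statistics will be presented by IMP and time point". It adds a general sentence: "For quantitative endpoints, Student test for parametric tests or Wilcoxon test for non-parametric tests will be used". Individual listings are by IMP, dose group, subject and time point.
- Section 12.3.1: "At each time point, the ECG will be recorded in triplicate, to reduce variance and improve the precision of measurement". QTcB is the routine correction; QTcF is calculated only when QTcB suggests prolongation.
- Table 3 (Part B) schedules an ECG at predose, T15' and H1. The PK row is also marked at predose and H1, and its H0 cell lists "T5', T15', T18', T30', T45". Amendment 3 thins the PK samples but keeps T15' ("Pharmacokinetics on Day 1 H0: T5', T15', T18', T30', T45").
- Section 9.5: "Subjects will be randomly assigned in Part B (Groups 3 to 8) in a 3:1 ratio to either MOTREM (LR12) or Placebo". With six groups of four (Section 9.1), that is 18 on LR12 and 6 on placebo.
- Modelling is mentioned only for pharmacokinetics (Section 15.2.1), and analysis of variance only for dose proportionality of PK parameters (Section 15.2.2).

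**The concern.** Safety and tolerability against placebo is the primary objective (Section 7.1), and ECG is one of the listed safety parameters. Loading doses in Part B span a factor of 10 and maintenance rates a wider one. If an ECG effect follows concentration, it will be largest at the end of the 5 mg/kg loading infusion. A single LR12 mean at that time mixes those subjects with others who had a tenth to two-fifths of the exposure. Tabulating each dose group separately avoids the mixing but leaves three active subjects per estimate. Neither summary uses the measured concentrations, although the ECG is replicated for precision and a PK sample is scheduled at the same nominal time. What is at stake is how well the trial can bound a QTc effect at its highest exposures, which Section 6.3 says will inform later patient studies.

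**Working it through.** The plan states no QTc precision, power or alpha to reproduce. Its planned size does reproduce: 2 x 1 + 6 x 4 = 26, of whom 24 are in Part B (18 LR12, 6 placebo).

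**Inputs from the documents.** Loading doses are 0.5, 1, 2, 5, 5 and 5 mg/kg over 15 minutes, so the top rate is 20 mg/kg/h. Maintenance rates are 0.03, 0.1, 0.3, 1, 3 and, for Group 8, 9 mg/kg/h (protocol) or 6 (Amendment 4); both were used. Monkey toxicokinetics suggest clearance within 15 to 30 minutes (Section 6.4.2.1). The later ECG and PK columns of Table 3 may be displaced in the extracted text, so only T15' and H1 were used.

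**Assumptions, not in the documents.** SD of a single-time QTc change 8 ms (range 6-10, with 12 as an extreme); within-subject correlation 0.5 (0.3-0.7); LR12 half-life 3-10 minutes; one-compartment linear kinetics; two-sided 90% CI; 10 ms as an illustrative threshold.

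**Step 1: dilution by pooling.** The top loading rate exceeds every maintenance rate, so the peak is at T15' and is proportional to the loading dose.
- At T15': mean(0.5, 1, 2, 5, 5, 5)/5 = 3.083/5 = 0.617. A 10 ms effect at the top peak, linear in concentration, would appear as about 6.2 ms.
- On the maintenance plateau, which H1 approximates in the higher-dose groups: 13.43/(6 x 9) = 0.25 with 9 mg/kg/h, or 10.43/(6 x 6) = 0.29 with 6 mg/kg/h.

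**Step 2: simple contrasts at T15'.** Half-width = t(0.95, n1 + n2 - 2) x SD x sqrt(1/n1 + 1/n2). At SD 8 ms:
- One dose group v pooled placebo (3 v 6): 1.895 x 5.657 = 10.7 ms.
- 5 mg/kg loading groups pooled (9 v 6): 1.771 x 4.216 = 7.5 ms.
- All LR12 (18 v 6): 1.717 x 3.771 = 6.5 ms. Scaled to the top peak: 6.48/0.617 = 10.5 ms.

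**Step 3: concentration-QTc model.** The columns are a T15' indicator, an H1 indicator, concentration (0 for placebo) and treatment, with equal correlation within subject. Variance of the predicted effect = c'(sum of X'V^-1 X)^-1 c, with c = (0, 0, peak concentration, 1). For half-life 3 minutes, correlation 0.5 and Group 8 at 9 mg/kg/h, the standard error is 4.05 ms. With 24 - 4 = 20 df, the half-width is 1.725 x 4.05 = 7.0 ms. Across the assumed half-lives, correlations and both Group 8 rates it is 6.6-7.0 ms. Allowing 25% between-subject variation in exposure gives 6.4-6.8 ms.

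**Step 4: range over SD.** Half-widths scale with the SD.

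| Analysis | SD 6 | SD 8 | SD 10 |
|---|---|---|---|
| All LR12 v placebo, scaled to peak | 7.9 | 10.5 | 13.1 |
| 3 v 6 | 8.0 | 10.7 | 13.4 |
| 9 v 6 | 5.6 | 7.5 | 9.3 |
| Model with treatment term | 5.2 | 7.0 | 8.7 |

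**Step 5: chance of an upper bound below 10 ms with no true effect** (noncentral t, SD 6 / 8 / 10 / 12; model at half-life 6 minutes, correlation 0.5, 25% exposure variation). Model: 0.95 / 0.79 / 0.62 / 0.50. 9 v 6: 0.91 / 0.73 / 0.56 / 0.44. 3 v 6: 0.68 / 0.48 / 0.36 / 0.28.

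**The case against.** The strongest objection is that the model buys little. Pooling the nine subjects who share the 5 mg/kg loading dose gives 7.5 ms against 7.0 ms, with no linearity assumption. With the residual SD pooled over the seven Part B arms (24 - 7 = 17 df) at SD 8 ms, 9 v 6 gives 7.3 ms and 3 v 6 gives 9.8 ms. This stands. The planned text does not specify that pooling, however, and it addresses only the shared peak, not the maintenance rates that differ between those groups.

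Second, the trial has no QTc objective, Section 15.4 intends mainly descriptive statistics, and the nonclinical sections report no adverse cardiovascular effect. This stands as a reason to keep the analysis exploratory and the point minor. A reader might infer that cardiac safety is left unexamined. It is not: every ECG is reviewed by a physician and abnormal values are flagged in the listings.

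Third, a reader might infer that ECG change is never tested. Section 15.1 allows a Student or Wilcoxon test on quantitative endpoints, so that reading is too strong. Such a test would compare LR12 with placebo and would still ignore concentration.

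Fourth, the bound is fragile. Pairing is nominal, and the order of assessments is left to the Study Operations Manual (Section 11.1). Over about two minutes of triplicates after T15', the top-group concentration could fall by 4-26% for half-lives of 10 to 3 minutes. A delayed effect regressed on the T15' concentration could look falsely reassuring. This stands and shapes the fix. Sample and ECG times are recorded, so the pairing can be checked.

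Fifth, Section 15.1 refers to a statistical analysis plan to be agreed by the sponsor, and no separate plan is in the text reviewed. If that plan already holds such a model, the point falls.

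**Conclusion.** The point holds as a minor, optional improvement. The planned IMP-by-time summary would show an effect linear in concentration at about 62% of its top-peak size, and nothing in the text uses the paired concentrations. At an assumed SD of 8 ms, modelling them narrows the 90% half-width at peak from about 10.5 ms (pooled summary scaled to peak) or 10.7 ms (one dose group) to about 7.0 ms. Against 9 v 6 the gain is only about 0.5 ms.

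A reader might infer that a 10 ms effect cannot be excluded under the present plan, or that the model would exclude it. Neither is supported. At SD 6 ms even 3 v 6 gives 8.0 ms, below 10 ms if the observed difference is zero. At SD 10 ms or more the model has at most a 0.62 chance of excluding 10 ms when there is no effect. The documents give no SD and no threshold. The 62% figure needs only the loading doses, dose-proportional peaks and a linear effect; the half-widths also rest on the assumed SD and, for the model, on the assumed correlation, half-life and an immediate effect.

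**What to change.** Keep the descriptive tables. Add one prespecified exploratory Part B analysis to the statistical analysis plan:

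1. A linear mixed model of baseline-adjusted QTc change on time-matched LR12 concentration (placebo = 0), with treatment and time terms.
2. QTcF derived for all records, since QTcB is routine and QTcF otherwise conditional.
3. Actual ECG and PK times, with a check of how closely each pair was taken.
4. The predicted effect with 90% CI at the observed mean peak of each loading dose.
5. As a check free of the linearity assumption, the three 5 mg/kg loading groups pooled (9) v pooled placebo (6) at T15'.

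The cost is a paragraph of plan text, derivation of QTcF and a little analysis work; no new measurement is needed. The remaining limits are nominal pairing, an assumed linear and immediate effect, and only a rough check for delay with two clearly matched times.

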#### Concomitant and other treatments:

Concomitant and other treatments are coded using the WHO-DRUG dictionary version 2014-3. All treatments continued after the inclusion or appeared during the study will be summarised by Anatomical Therapeutic Class (ATC) and substance name.

#### Anti- LR12 antibodies:

Anti- LR12 antibodies results (positive/negative) will be listed.

## 15.2 Pharmacokinetics

### 15.2.1 Evaluation of Pharmacokinetic Parameters

Non-compartmental analysis will be used for estimation of pharmacokinetic parameters using the SAS software. Pharmacokinetic modelling may also be employed to assess potential time-dependent pharmacokinetics.

The following pharmacokinetic parameters will be calculated from measured plasma concentrations of LR12 for each subject and each treatment group:

#### **Cmax and tmax**

Cmax : Maximal plasma concentration  
tmax : Time at which the maximum plasma concentration occurs  
C0.25h : Concentration at the end of the loading infusion  
C8h : Concentration at the end of the maintenance infusion  
Css inf : Steady state concentration during the maintenance infusion

#### **Area under the curve (AUC)**

AUC(0-8h) : Area under the plasma concentration-time curve from time 0 to time 8 h (ng/ml.h)  
AUC(0-t) : Area under the plasma concentration curve from administration to last observed concentration at time t measured by trapezoidal rules (ng/ml.h)  
AUC(0-∞) : Area under the plasma concentration-time curve from time 0 extrapolated to infinite time (ng/ml.h)  
[AUC0-∞ = AUC0-t + (Ct/λz), where Ct = the observed concentration of drug for the last sample on the PK profile in which drug was detected, and λz as defined below]

#### **Plasma concentration half-life**

t1/2 (h) : Terminal elimination half-life. It will be calculated by application of the equation:  
$$t_{1/2} = \ln 2 / \lambda_z$$
  
λz (1/h) : Will be estimated by the linear regression of the logarithm of the terminal concentration as a function of time  
CL(L/h/kg) : Apparent systemic clearance  
Vd (L/kg) : Apparent volume of distribution (CL/λz)

Actual sampling times will be used for all calculations of the PK parameters. If there is any doubt in the actual time a sample was taken, then the scheduled time will be used. Special

consideration will be given to the estimation of  $\lambda_z$  and corresponding  $t_{1/2}$  values. Values of  $\lambda_z$  will be calculated from a minimum of three data points, wherever possible. Any values below the lower limit of quantification (LLOQ) of the assay before the  $t_{max}$  will be assumed to be zero. Values below the LLOQ which occur after the  $t_{max}$  will be ignored.

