#### **6.4.2 Potential Risks**

##### **6.4.2.1 Nonclinical Safety Pharmacology and Toxicology:**

Toxicity studies were only conducted in one species in accordance with ICH guidance documents S6(R1) and M3(R2) as well as to EMA’s guidance on repeated dose toxicity (EMEA/CHMP/SWP/488313/2007). Safety pharmacology also followed the ICH S7A and S7B guidance.

A cardiovascular safety study in Cynomolgus monkeys did not identify any adverse cardio-vascular effect of LR12, when administered as an intravenous infusion of 18-times the expected pharmacologically active dose. In addition, the central nervous and pulmonary systems were explored during the toxicity studies and did not unveil untoward effects.

Receptor binding assays with a wide range of receptors did not show any relevant off target effects in vitro.

A bacterial reverse mutation test (Ames test) and a chromosome aberration test did not show any evidence for genotoxicity of LR12.

Toxicokinetic studies showed dose-dependent kinetics and suggested a clearance of the product within 15 to 30 minutes depending on the dose.

A series of toxicity studies was conducted with LR12 in cynomolgus monkey, as this represents the only relevant species. In the pivotal 14-day toxicology study with the clinical formulation, the administration of LR12 was safe and well tolerated at doses 7.2, 24 and 140 mg/kg/day. No adverse events were observed up to the highest dose level. In addition, a dose of 440 mg/kg/day in a preliminary formulation was found to be safe and well tolerated in a 14-day study.

Severe time dependent adverse events, likely related to immunogenicity, were observed in the low- dose arm of an early toxicity study conducted with an experimental frozen formulation that was diluted with a technical, non USP grade buffer. Further toxicology studies with a suitable buffer or the API alone and with the final clinical formulation did not reproduce these findings.

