## **8.4 Rationale for Study Design, Doses and Control Groups**

This study is the first time that MOTREM will be given to healthy young subjects.

A standard single dose escalation design is used for this study to evaluate the safety, tolerability and PK of the investigational product in healthy subjects. The study is randomised and double blind (Part B only) to minimise bias and includes placebo to facilitate identification of effects related to administration of drug rather than the study procedures or situation.

For the first two dose levels (Part A) there will be no placebo and only one subject will be dosed, as these dose levels are well below the expected therapeutic dose range and expected to be below the limit of quantification in human blood and therefore not considered informative (9).

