### **Human Equivalent Dose (HED) Calculation**

According to the “Guidance for Industry: Estimating the Maximum Safe Starting Dose in Initial Clinical Trials for Therapeutics in Adult Healthy Volunteers. FDA/CDER, July 2005”, normalisation to body surface area is an appropriate method for extrapolating doses between species (hereafter referred to as “HED BS”). However, certain exceptions are made. It is considered that scaling based on body weight (i.e. setting the HED (mg/kg) = NOAEL (mg/kg) and referred to in this document as “HED BW”) may be appropriate for therapeutics that will have little distribution outside the intra-vascular compartment. There is some evidence that LR12 mainly remains in the i.v. compartment after administration. However, distribution of LR12 is not yet fully characterised.

On the other hand, the clearance of LR12 is very fast in monkeys and it is expected to be similar in humans. Since LR12 is planned to be administered continuously by i.v. infusion to maintain steady state concentrations, as it has been done in efficacy pharmacology models, it is necessary to consider exposure time to LR12 at a given plasma concentration/infusion rate in order to determine appropriate safety margins.

For the above mentioned reasons, both approaches HED BS and HED BW will be taken into consideration as well as rate of infusion and time of exposure in order to calculate the safety margin for this FIH study.

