**Table 8. Planned Dose Escalation Scheme.**

Group	Loading dose			Maintenance dose		
	(mg/kg) 15 min	Rate (mg/kg/h)	Total (mg)*	Rate (mg/kg/h)	Total 7h45 (mg/kg)	Total 7h45 (mg)*
1	0.014	0.057	1	-	-	-
2	0.140	0.570	10	-	-	-
3	0.500	2.000	35	0.03	0.23	16.3
4	1.000	4.000	70	0.10	0.78	54.3
5	2.000	8.000	140	0.30	2.33	162.8
6	5.000	20.000	350	1.00	7.75	542.5
7	5.000	20.000	350	3.00	23.25	1,627.5
8	5.000	20.000	350	9.00	69.75	4,882.5

\*Assuming a body weight of 70kg

The second dose planned to be administered to humans is 10 mg as a “loading” dose infused i.v. for 15 minutes. This will be equivalent to a rate of infusion of 0.57 mg/kg/h and to 0.14 mg/kg dose for an individual of 70 kg.

According to this, the second cohort dose rate in mg/kg/h will be 3.3 times lower than the NOAEL HED BS (1.88 versus 0.57) and 10 times lower than the NOAEL HED BW (5.83 versus 0.57). In terms of total exposure, knowing that the reference taken in toxicology studies is of 24 hours and that total exposure time for this cohort will be 15 minutes, the total exposure in a one-day period in mg/kg will be 323 times lower on the basis of HED BS (45.16 versus 0.14) and 1000 times lower on the basis of HED BW (140 versus 0.14).

If the highest loading dose given during the toxicology study is considered, the second cohort dose in mg/kg/h will receive a 45 times lower dose by HED BS conversion (25.81 versus 0.57) and a 140 times lower dose according to HED BW (80 versus 0.57). The total exposure in a 15 minutes period in mg/kg will be 46 times lower on the basis of HED BS (6.45 versus 0.14) and 143 times lower on the basis of HED BW (20 versus 0.14).

From cohorts 3 to 6, the loading dose will be increased incrementally by a factor 2 (or 2.50).

The first maintenance dose rate will be introduced in cohort 3 and is of 16.3 mg at an infusion rate of 0.03 mg/kg/h for a total exposure time of 7h45. This corresponds to 0.23 mg/kg dose for an individual of 70 kg.

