### **15.2.2 Statistical Analysis on PK Parameters**

Serum concentrations will be listed and summarised by time point. The PK parameters will be listed for each subject and summarised for each treatment group using descriptive statistics (N - the number of subjects, arithmetic mean, SD - standard deviation, CV - coefficient of variation, geometric mean, median, minimum, maximum).

Analysis of variance models will be applied to the dose normalised and logarithmically transformed pharmacokinetic parameters to investigate possible deviations from dose proportionality.

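### Section 15.2.1 applies its post-tmax LLOQ rule and its AUC0-∞ extrapolation while the Part B infusion is still running, so AUC0-∞ can be wrong in either direction when the plateau is below or just above the LLOQ

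*Combined protocol and SAP*

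**What the plan says.** Section 15.2.1 sets values below the LLOQ before tmax to zero. "Values below the LLOQ which occur after the" tmax are ignored. AUC0-∞ is AUC0-t plus Ct/λz, where Ct is "the observed concentration of drug for the last sample on the PK profile in which drug was detected". λz comes from a log-linear regression on terminal concentrations, with at least three points wherever possible, and the section promises special consideration of its estimation. Nothing in the section mentions the end of infusion.

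Section 15.2.2 then uses the parameters to look for departures from dose proportionality: "Analysis of variance models will be applied to the dose normalised and logarithmically transformed pharmacokinetic parameters".

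Table 8 gives the Part B regimens, each a 15-minute loading dose followed by 7 h 45 min of maintenance. Below it the plan states: "The first maintenance dose rate will be introduced in cohort 3 and is of 16.3 mg at an infusion rate of 0.03 mg/kg/h".

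Three passages bear on whether the plateau can be measured:
- Section 8.4 says the two Part A doses are "expected to be below the limit of quantification in human blood and therefore not considered informative".
- Section 6.4.2.1 says: "Toxicokinetic studies showed dose-dependent kinetics and suggested a clearance of the product within 15 to 30 minutes depending on the dose".
- Section 8.4.1 says "the clearance of LR12 is very fast in monkeys and it is expected to be similar in humans".

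The LLOQ, the human half-life and the formula for CL are not stated. Section 15.3 covers unrecorded values, not results below the LLOQ. Section 15.5 refers to a separate analysis plan for the interim analysis, which is not among the documents.

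**The concern.** A rule anchored to tmax suits a profile in which drug input has stopped by the time of the peak. Part B is different: the peak comes at the end of loading, and almost eight hours of input follow.

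If the plateau cannot be quantified, ignoring those samples and extrapolating from the last detected one treats dosing as finished within the first hour. Most of the maintenance dose drops out of AUC0-∞. If the plateau can be quantified but too few post-infusion samples can, the regression for λz picks up flat infusion samples. λz is then far too small, and Ct/λz far too large.

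The affected values would go into the dose-normalised analysis of variance next to nearly unbiased values from other groups. That could suggest non-proportionality under linear kinetics, or hide it where it exists.

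**Working it through.** **1. The plan's own figure.** Group 3 maintenance is 0.03 × 7.75 = 0.2325 mg/kg; × 70 kg = 16.275 mg, which matches the stated 16.3 mg. Loading is 0.5 × 70 = 35 mg, as in Table 8.

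**2. Where tmax falls.** Loading rate over maintenance rate (Table 8): Group 3, 2/0.03 = 67; Group 4, 4/0.1 = 40; Group 5, 8/0.3 = 27. The peak is the end of loading.

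**3. Loading share, L/(L + 7.75 M), assuming linear kinetics.**
- Group 3: 0.5/0.7325 = 68%
- Group 4: 1/1.775 = 56%
- Group 5: 2/4.325 = 46%

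**4. Model.** Noise-free, one compartment, CL = 1, so that concentration is in infusion-rate units and the plateau equals M. Samples are at the Table 3 times, the rules are as written, the trapezoid is linear, and λz comes from the last three quantifiable points (two where only two exist). Group 8 is run at 6 mg/kg/h (Amendment 4). The half-life is an assumption: clearance in 15–30 min in animals, read as 3–5 half-lives, gives 15/5 = 3 to 30/3 = 10 min. The main range is 5–10 min.

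**5. Can the plateau be below the LLOQ?** The 10 mg infusion rate is 10/70/0.25 = 0.571 mg/kg/h. Its peak is 0.571 × (1 − 2^(−15/h)), with h the half-life in minutes: 0.500 at 5 min, 0.369 at 10 min. Divided by the plateaus 0.03, 0.1 and 0.3, this is 16.7, 5.0 and 1.7 (5 min) or 12.3, 3.7 and 1.2 (10 min). So if the 10 mg peak is below the LLOQ, the plateaus of Groups 3–5 are too. Group 3 stays below until the 10 mg peak exceeds about 12–17 times the LLOQ. Solving peak = plateau, the inference fails only for half-lives above about 193, 54 and 14 min in Groups 3, 4 and 5.

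**6. Plateau below LLOQ, worked case.** Group 5, 5 min, LLOQ 0.500.
- Concentrations: 4.00 (T5'), 7.00 (T15'), 4.72 (T18'), 1.14 (T30'). T45' is 0.405, so it is ignored with the rest of the plateau.
- AUC0-t = 0.167 + 0.917 + 0.293 + 0.586 = 1.962.
- Fitted λz = 7.22/h (true 8.32/h). Ct/λz = 1.1375/7.22 = 0.157.
- AUC0-∞ = 2.12 against a true 4.325, or 49%.

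For half-lives of 5–10 min and any LLOQ from 1.2 times the plateau up to the 10 mg peak, Groups 3, 4 and 5 read 66–74%, 59–63% and 49–54% of truth.

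**7. Plateau just above LLOQ.** The first two post-infusion samples, at 2 and 4 min, are quantifiable only if plateau/LLOQ exceeds 2^(2/h) and 2^(4/h): 1.32 and 1.74 at 5 min, 1.15 and 1.32 at 10 min.
- Below the first limit there is no post-infusion point. λz is fitted to a flat line and AUC0-∞ is meaningless.
- Between the limits there is one. Worked case: Group 5, 5 min, plateau 1.5 times the LLOQ. The three points are H6 (0.300), T-15' (0.300) and T2' (0.227). Fitted λz = 0.088/h and Ct/λz = 0.227/0.088 = 2.58. AUC0-t is 4.35, so AUC0-∞ = 6.93, or 160% of truth. AUC0-t itself is 101%.
- Across Groups 3–6 the one-point case reads 137–168% at 5 min and 183–255% at 10 min.
- At about twice the LLOQ or more, all groups read about 100–104% at both half-lives.

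**8. Worst case for Part A.** With the 10 mg peak at the LLOQ and a 5 min half-life, Groups 3–8 read 66, 59, 49, 104, 100 and 100%.

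**The case against.** The trigger is not established. Amendment 2 adds a subject to learn more about kinetics at 10 mg, section 8.2.4 frames Part B escalation in terms of Cmax and the steady-state concentration, and Table 3 schedules a plateau sample. All of this suggests that some levels were expected to be measurable. Slower elimination also shrinks the problem: at a 20-minute half-life Group 5 is nearly unbiased even with the 10 mg peak at the LLOQ. This stands, and the point is conditional.

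The plan calls λz terminal and promises special consideration, so a careful analyst might not fit it to infusion samples. Some Group 3 results, including the 66%, rest on a two-point slope that an analyst might decline to report. This stands too. It makes the defect a gap in the written rule rather than a deliberate choice of a biased method, but the text states no safeguard.

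The consequence is limited. Kinetics is a secondary objective, section 15.4 plans mostly descriptive statistics, there are three active subjects per group, and listings and individual plots would show an empty plateau. That lowers the severity, but the rule would still yield a parameter value.

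A reader might infer a simple step, with low-dose groups understated and every group with a quantifiable plateau sound. Step 7 of the working rules that out: a barely quantifiable plateau gives errors upward. A reader might also infer that CL and Vd are overstated. The documents do not support that, because no CL formula is given. The abbreviation list includes an infusion rate and a steady-state concentration, and CL formed from those two would be not estimable rather than inflated.

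**Conclusion.** The point holds conditionally. As written, section 15.2.1 gives a wrong AUC0-∞ for any Part B group whose plateau is below, or only slightly above, the LLOQ. Below it, AUC0-∞ is roughly the loading share: 68%, 56% and 46% in Groups 3–5 from Table 8 under linear kinetics, or 66–74%, 59–63% and 49–54% modelled. Just above it (about 1.0–1.7 times at 5 min, 1.0–1.3 times at 10 min), AUC0-∞ is about 137–255% of truth in Groups 3–6 or meaningless. From about twice the LLOQ it is nearly right.

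These sizes rest on linear one-compartment kinetics without noise and on an assumed 5–10 minute half-life; section 6.4.2.1 mentions dose-dependent kinetics in animals. The bias has no single direction, so the documents do not support saying that proportionality will be falsely rejected. No error rate can be given without the variability, significance level and assay error. If CL were computed as dose/AUC0-∞, the below-LLOQ case would overstate it by about 1.47, 1.78 and 2.16 times (0.7325/0.5, 1.775/1, 4.325/2), but that formula is not stated.

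Severity is minor to moderate, for a secondary objective.

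**What to change.** In section 15.2.1 or the analysis plan:
- Limit the ignore rule to values below the LLOQ after the end of the maintenance infusion.
- Take λz and Ct only from samples after the end of infusion.
- Where the last quantifiable sample precedes the end of infusion, or fewer than three post-infusion samples are quantifiable, report λz, t1/2, AUC0-∞ and any CL or Vd derived from them as not estimable. Leave them out of the proportionality model.
- Where the plateau is below the LLOQ, also report the steady-state concentration and C8h as <LLOQ, and AUC0-8h as not estimable.
- Where the plateau is quantifiable, still report AUC0-8h or AUC0-t.

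The cost is a few sentences and no new samples. Some low-dose parameters become not estimable, so the proportionality model may have fewer dose groups for AUC0-∞. Groups with only one or two post-infusion points lose AUC0-∞ but keep AUC0-8h or AUC0-t.
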